
The following aims and hypotheses will be addressed in this proposal.

Specific Aim 1: To identify impairments in neural systems underlying comorbid AUD/ET by examining fMRI response during a dynamic SEP task

Hypothesis: Ventromedial prefrontal cortex (VmPFC) (stress-baseline). The AUD/ET group will display a lack of dynamic VmPFC response in the Late-Stress period.

Hypothesis 1b: Ventral Striatum (VS) (alcohol cue-baseline). The AUD/ET group will show decreased VS activity during alcohol cue exposure, while AUD/NT group show increased VS response to alcohol cue.

Specific Aim 2: To evaluate neural correlates of HPA axis response using a validated fMRI and HPA approach

Hypothesis 2. Lower dynamic VmPFC response to stress will be associated with blunted cortisol response to stress (stress-baseline) across groups.

Specific Aim 3: To examine whether impaired neural responses during the SEP task predict future relapse after treatment during the 90-day follow-up

Hypothesis 3. Lower dynamic VmPFC response to stress will predict early relapse.

2. Probable Duration of Project:

Duration of the project: 5 years (recruiting 160 participants)

A total of 160 subjects (ages 21-50) will be recruited including four demographically-matched groups (N=40 each; equal sex ratio) of 80 treatment-seeking AUD patients with and without early trauma (AUD/ET, AUD/NT) and 80 moderately drinking controls with and without early trauma (MD/ET, MD/NT). An experiment is proposed using a 2 (AUD, MD) X 2 (ET, NT) x 3 (Condition: Stress, Alcohol, and Neutral) mixed factorial design with the first two factors (Groups) as between-subjects factors and Condition as a within-subjects factor. Equal genders will be included in each group, and the effects of gender will be assessed. All AUD patients will be scheduled for a multimodal fMRI scan during acute abstinence within 3-5 days of last drink. Then patients will receive an 8-week outpatient treatment and scheduled for a second scan in the 8th week of the treatment. Moderate drinking controls will participate in a single MRI session after baseline assessments.

Duration of study participation:

AUD patients: 22 weeks (baseline/MRI session (2 weeks), outpatient treatment (8 weeks) + follow-up (12 weeks))

Control subjects: 6 weeks (baseline/MRI session (2 weeks), follow-up (4 weeks))

3. Background:

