E. Can donor-subjects withdraw their materials at any time, and/or withdraw the identifiers that connect them to their materials? *Write here*

- i. How will requests to withdraw materials be handled (e.g., material no longer identified: that is, anonymized) or material destroyed)? *Write here*

F. Describe the provisions for protection of participant privacy *Write here*

G. Describe the methods for the security of storage and sharing of materials *Write here*

6. **Subject Population:** Provide a detailed description of the types of human subjects who will be recruited into this study.

A total of 160 participants (ages 21-50) including four demographically-matched groups (N=40 each; equal sex ratio) of 80 treatment-seeking AUD patients with and without early trauma (ET) (AUD/ET, AUD/NT) and 80 moderately drinking controls with and without early trauma (MD/ET, MD/NT).

7. **Subject classification:** Check off all classifications of subjects that will be specifically recruited for enrollment in the research project. Will subjects who may require additional safeguards or other considerations be enrolled in the study? If so, identify the population of subjects requiring special safeguards and provide a justification for their involvement.

 Children	 Healthy	 Fetal material, placenta, or dead fetus
 Non-English Speaking	 Prisoners	 Economically disadvantaged persons
 Decisionally Impaired	 Employees	 Pregnant women and/or fetuses
 Yale Students	 Females of childbearing potential	

NOTE: Is this research proposal designed to enroll children who are wards of the state as potential subjects?

Yes No

8. **Inclusion/Exclusion Criteria:** What are the criteria used to determine subject inclusion or exclusion?

Inclusion Criteria:

- (1) men and women, aged 21-55 years (equal sex ratio)
- (2) presence of AUD and early trauma (ET) to match one of the following four groups: AUD with ET, AUD with NT (no trauma), MD (moderate drinkers) with ET, MD with NT

<AUD> meets DSM-V criteria for either moderate or severe Alcohol Use Disorder (AUD).

Regular alcohol use over the past year of, at least 8 standard drinks/week for women and at least 15 standard drinks/week for men (binge drinking allowed).

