<MD> never meets DSM-V criteria for AUD

Regular alcohol use over past year not to exceed 7 standard drinks/wk for women and 14 standard drinks/wk for men, with no occasions of binge drinking

<ET> scores above "moderate to severe" range (based on CTQ cut score).

<NT> No history of ET ("non-to-low" range (based on CTQ total score)

(3) good health as verified by physical health exam and lab tests

(4) abstinence of drug use and alcohol in the 72 hours prior to MRI scan

(6) body mass index (BMI) up to 35 (to limit morbid obesity related medical conditions and weight limitations of the MRI scanner)

(7) provide negative breathalyzer and urine toxicology screens at all appointments

(8) able to read/write English, provide informed written/verbal consent, and complete study evaluations

Exclusion Criteria:

(1) current or past substance use disorder other than alcohol; also excluding caffeine and nicotine

(2) current psychiatric disorders; current use of psychiatric medications, including anxiolytics, antidepressants, naltrexone or Antabuse

(3) past psychiatric disorders; except for mood and anxiety disorders (including PTSD) that are highly comorbid with early trauma

(4) any significant current medical condition such as neurological, cardiovascular, endocrine, renal, liver, thyroid pathology; subjects on medications for any medical condition

(5) women on oral contraceptives; peri- and post- menopausal, pregnant (as assessed by a pregnancy test during initial medical evaluation) or lactating women.

(6) history of prior loss of consciousness or brain injury

(7) significant visual or hearing impairment

(8) MRI specific exclusion criteria

(i) history of claustrophobia due to confined MRI scanning environment

(ii) left-handed individuals for the fMRI due to variation in laterality of neuroimaging response resulting from difference in handedness

(iii) have implanted metal in their bodies that would be affected by the strong magnetic field during MRI session (examples: cardiac pacemaker, implanted pacing wires, implanted medication pumps, metal fragments in eyes, intracranial aneurysm clips, cochlear implant, retinal tack, recently implanted metal clips, shunts, rods, or plates; other ferromagnetic implants above the level of the clavicle, implanted electrodes or neural stimulator, claustrophobia, and orthodontic braces or permanent retainer wires)

9. How will eligibility be determined, and by whom? Write here

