For the current study, the following individuals, funding, and/or regulatory agencies will be notified:

- All Co-Investigators listed on the protocol.
- Yale Cancer Center Data and Safety Monitoring Committee (DSMC)
- National Institutes of Health (National Institute on Alcohol Abuse and Alcoholism)
- Food and Drug Administration (Physician-Sponsored IND #_____)

- Medical Research Foundation (Grant _____)
- Study Sponsor
- Other Data Safety Monitoring Board (DSMB) or Committee (DSMC)

The principal investigator will conduct a review of all adverse events upon completion of every study subject. The principal investigator will evaluate the frequency and severity of the adverse events and determine if modifications to the protocol or consent form are required.

13. Statistical Considerations: Describe the statistical analyses that support the study design.

Procedures for data management will follow the YSC and Yale MRRC procedure, and we will use Research Electronic Data Capture (REDCap), a HIPPA compliant, secure web application. The data analytic plan described below focuses on testing the specific hypotheses in the Aims section.

Behavioral Data Analysis: fMRI task ratings (stress, craving) will be analyzed using linear mixed models, with two groups (AUD, ET) as between-subjects factors and Condition (Alcohol, Stress, Neutral) as within-subjects factors.

Analysis of Stress Hormone: For plasma samples, assay processing will be conducted using standard radioimmunoassay procedures used in our prior work [3,20] at the Core Laboratory of the Yale Center for Clinical Investigation. We will also assess maximal or peak response and area under the curve for each measure, which are commonly used in the literature (e.g., [20]).

Analysis of HRV and Eye Tracking: HR and HRV data will be processed and analyzed using MATLAB and Kubios HRV software. For HRV, the root mean square of successive differences (RMSSD) will be calculated from beat-to-beat intervals. Eye tracking data will be analyzed using R and MATLAB. Position changes of the eye in the X-Y plane will be recorded, and fixation location, duration and count will be calculated during picture viewing.

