Aim 2: neural correlates of HPA axis function: For basal cortisol levels, a 2×2 factorial design will be applied with AUD (AUD, MD) and ET (ET, NT) as the between-subjects factors. For changes in stress hormone (cortisol, ACTH) during the SEP task, all data analyses will use change from baseline (provocation minus baseline) values. Then, a $2 \times 2 \times 3$ mixed-factorial design will be used with AUD (AUD, MD) and ET (ET, NT) as the between-subjects factors and Condition (Alcohol, Stress, Neutral) as the within-subjects factors. In addition, to examine the associations between task-related brain activity and stress hormone response, whole-brain correlation analyses will be conducted using BioImageSuite.

Aim 3: neural correlates of relapse: As reported in our previous papers [15,19,20], the primary outcome of relapse and treatment will be time to relapse (event based) and secondary outcome will be percent days of alcohol use during the follow-up period. These measures will also be assessed for their sensitivity and specificity of relapse risk prediction and treatment outcome over and above clinical and demographic measures associated with relapse and treatment outcome. For event-based relapse outcome measures (time to relapse, time to heavy drinking relapse), Cox proportional hazards regression (PHREG) models will be implemented for the primary predictor variable of dynamic VmPFC response controlling for any significant clinical, alcohol history or demographic measures that predict relapse [15,20].

SECTION II: RESEARCH INVOLVING DRUGS, BIOLOGICS, RADIOTRACERS, PLACEBOS AND DEVICES

If this section (or one of its parts, A or B) is not applicable, check off N/A and delete the rest of the section.

A. RADIOTRACERS **N/A**

1. Name of the radiotracer: *Write here*
2. Is the radiotracer FDA approved? **YES** **NO**

If NO, an FDA issued IND is required for the investigational use unless RDRC assumes oversight.

9. Check one: IND# *Write here* or RDRC oversight (RDRC approval will be required prior to use)
4. **Background Information:** Provide a description of previous human use, known risks, and data addressing dosage(s), interval(s), route(s) of administration, and any other factors that might influence risks. If this is the first time this radiotracer is being administered to humans, include relevant data on animal models.
Write here
4. **Source:** Identify the source of the radiotracer to be used. *Write here*

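### The gender effect that the plan promises may be confounded with age, and no behavioral, Aim 1 or Aim 2 model contains age or sex; if these are matched and prognostic, the between-group tests are also mildly conservative

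*Combined protocol and SAP*

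**What the plan says.** All references are to the combined protocol and SAP.

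- **Design (item 2, Probable Duration of Project).** The study has "four demographically-matched groups (N=40 each; equal sex ratio"). On gender the commitment is: "Equal genders will be included in each group, and the effects of gender will be assessed". No model, contrast or test for gender follows, there or later.
- **Age range.** Item 2 and item 6 (Subject Population) give 21 to 50: "A total of 160 participants (ages 21-50) including four demographically-matched groups". Item 8, inclusion criterion 1, gives "men and women, aged 21-55 years (equal sex ratio").
- **Exclusion 5 (item 8).** It bars "women on oral contraceptives; peri- and post- menopausal, pregnant" and lactating women. Men have no corresponding restriction.
- **Models (item 13, Statistical Considerations).** Behavioral ratings use "linear mixed models, with two groups (AUD, ET) as between-subjects factors and Condition (Alcohol, Stress, Neutral) as within-subjects factors". Aim 1 uses a 2 x 2 x 3 3dLME with the same three factors, followed by voxel-wise two-sample t tests. For basal cortisol in Aim 2, "a 2×2 factorial design will be applied with AUD (AUD, MD) and ET (ET, NT) as the between-subjects factors"; hormone change adds Condition as a within-subject factor. The Aim 2 brain-hormone association is a whole-brain correlation with no covariate stated.
- **The exception.** The Aim 3 Cox model admits demographic measures, but only those found to be significant predictors of relapse.

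Apart from the equal sex ratio, the matching variables are not named.

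**The concern.** Two separate consequences follow from leaving age and sex out.

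First, an equal sex ratio balances the number of men and women but not their ages. Exclusion 5 acts on women alone and removes them unevenly by age. Matching the four AUD/ET groups to each other does nothing about a difference between the sexes that is present within every group. A gender comparison without age may then partly be an age comparison. A sex term alone would not cure this.

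Second, matching removes the matched variable from the group contrast. If that variable is then left out of the model, its variance stays in the residual. The standard error describes groups that were not matched, so the test is conservative and some of the precision that matching bought is lost.

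**Working it through.** **Plan's own figures.** 4 groups x 40 = 160, which agrees with "Duration of the project: 5 years (recruiting 160 participants"). With an equal sex ratio that is 20 men and 20 women per group, 80 against 80 overall. The plan gives no power, effect size, SD or age-outcome correlation, so everything below rests on stated assumptions.

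**A. Age gap between the sexes, late exclusion only.** Assume uniform ages from 21, men up to 50 or 55, and women up to an effective upper age *w* of 43, 47 or 49.

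- Gap = (men's upper age − *w*)/2.
- Pooled SD = √{[(men's upper age − 21)² + (*w* − 21)²]/24}.
- Example, men to 50 and *w* = 43: gap 3.5 years, SD √[(29² + 22²)/24] = 7.43, so 3.5/7.43 = 0.47 SD.

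| Men to | w = 43 | w = 47 | w = 49 |
|---|---|---|---|
| 50 | 3.5 y (0.47 SD) | 1.5 y (0.19 SD) | 0.5 y (0.06 SD) |
| 55 | 6.0 y (0.73 SD) | 4.0 y (0.46 SD) | 3.0 y (0.33 SD) |

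Age contribution to the gender difference = r x standardised gap, with the age-outcome correlation r assumed to be 0.1 to 0.3. The SE for 80 against 80 is √(2/80) = 0.158 SD.

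- Men to 50: 0.01 to 0.14 SD. A nominal 5% gender test would reject in about 5 to 14.5% of studies with no true gender effect. At the top: 0.141/0.158 = 0.89, and Φ(0.89 − 1.96) + Φ(−0.89 − 1.96) ≈ 0.145.
- Men to 55: 0.03 to 0.22 SD, rejecting in about 5.5 to 28%.

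**B. The same gap with the other part of exclusion 5.** Users of oral contraceptives and pregnant or lactating women are likely to be mostly younger. Assume this removes 25% or 40% of women aged 21 to 35. Example, 25% and *w* = 43: ages 21 to 35 carry 14 x 0.75 = 10.5 units at mean 28, and ages 35 to 43 carry 8 units at mean 39. The women's mean is (10.5 x 28 + 8 x 39)/18.5 = 32.8. Men to 50 have mean 35.5, so the gap is 2.7 years.

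| Men to | Removed | w = 43 | w = 47 | w = 49 |
|---|---|---|---|---|
| 50 | 25% | 2.7 y | 0.6 y | −0.5 y |
| 50 | 40% | 2.1 y | −0.1 y | −1.3 y |
| 55 | 25% | 5.2 y | 3.1 y | 2.0 y |
| 55 | 40% | 4.6 y | 2.4 y | 1.3 y |

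With a ceiling of 50 even the sign is uncertain. With 55 the men stay older throughout this range.

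**C. Between-subject group contrasts.** Let R² be the share of outcome variance explained by a variable that is matched but left out of the model.

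- SE ratio f = 1/√(1 − R²).
- True size = 2[1 − Φ(1.96 f)].
- Power, where the adjusted test would have 80%, = Φ(2.80 − 1.96 f). The matched contrast really does vary less than the model believes, so only the critical value is inflated.

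| R² (assumed) | f | True size | Power |
|---|---|---|---|
| 0.05 | 1.026 | 4.4% | 78.5% |
| 0.10 | 1.054 | 3.9% | 76.9% |
| 0.20 | 1.118 | 2.8% | 72.9% |

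A simulation of the 2 x 2 with 40 per cell (4,000 runs) gave sizes of 4.3%, 3.5% and 2.9% without age in the model, and 4.8%, 4.5% and 5.2% with it. Without age matching, at R² = 0.10, the SE ratio was 1.01 and the size 5.0%.

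**D. Group x Condition contrasts.** An age effect that is the same in every condition cancels within the subject. Simulated at R² = 0.20 (3,000 runs), the SE ratio was 1.01 and the size 5.0%, so there is no distortion.

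**The case against.** The strongest reply is that the documents support neither a definite bias nor a definite error in the standard errors. Much of that stands.

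- A reader might infer that women in every group will be younger than men. That follows only from the menopausal part of exclusion 5. The rest of the criterion probably removes younger women and pulls the other way (part B). Under a ceiling of 50 the documents fix neither size nor sign.
- A reader might infer that the gender analysis is biased. No gender model is written, so none can be called biased, and gender appears in no aim or hypothesis. What can be said is that the analysis is unspecified and open to confounding by age.
- A reader might infer that the standard errors are too wide outright. This needs the omitted variable to be balanced across groups and to predict the outcome. For sex, the equal ratio meets the first condition if achieved; for age, nothing says it was a matching variable. No figure supports the second condition for either, and nothing supports an R² as high as 0.20.
- The hypotheses and the hormone analysis use differences from baseline. A constant age effect cancels there, and only an effect of age on reactivity remains.
- The error in the group tests is on the safe side: it neither biases the contrasts nor inflates type I error.

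What does not fall away: exclusion 5 has no counterpart in men, matching is not described between the sexes, a gender assessment is promised, and no behavioral, Aim 1 or Aim 2 model has an age or sex term.

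**Conclusion.** The concern holds in a limited form.

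**Gender.** The promised effect may be confounded with age. Under the assumptions in part A the contribution runs from near zero to 0.14 SD with men to 50, and from 0.03 to 0.22 SD with men to 55, against an SE of 0.158. Allowing for the loss of younger women reduces the gap and, with a ceiling of 50, can reverse it. Upper ages, age distribution, proportions removed and correlations are all assumptions.

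**Group tests.** If age or sex is matched and prognostic, the between-subject AUD, ET and AUD x ET tests are conservative; this includes basal cortisol and the voxel-wise two-sample t tests. The cost is one and a half to three points of power at R² of 0.05 to 0.10, and about seven at 0.20. Group x Condition terms are untouched unless the covariate effect differs by condition. In the Aim 2 brain-hormone correlation the issue is different: omitted age or sex is a possible confounder of the association.

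This is a worthwhile improvement, not a threat to the main comparisons.

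**What to change.** - Name the variables used to match the four groups.
- Prespecify mean-centred age, sex and any other matching variable as between-subject covariates in the behavioral mixed model, the 3dLME and its follow-up contrasts (in place of unadjusted t tests), the basal-cortisol 2 x 2, the hormone-change 2 x 2 x 3 and the Aim 2 brain-hormone association.
- State the gender contrast and estimate it from these age-adjusted models. Add a sensitivity analysis restricted to the age range that both sexes actually cover.
- Reconcile the age range in items 2 and 6 with inclusion criterion 1.

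The cost is SAP wording and slightly more analysis. Age and sex are needed for eligibility, so no new data are required. The 2 x 2 leaves 160 − 4 = 156 degrees of freedom; age and sex use two, and each further matching variable one or a few more.

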Alcohol withdrawal will be measured using the Clinical Institute Withdrawal Assessment of Alcohol Scale, Revised (CIWA_Ar) (Sullivan et al., 1989). CIWA-Ar is a 13-item interviewer guided measure to evaluate current alcohol withdrawal (AW) signs and symptoms. The assessment includes objective measures (e.g., pulse), participants' responses to questions, such as orientation to time and space ("What day is this? Where are you? Who am I?"), and observations by the interviewer (evidence of tremor or paroxysmal sweats). Item responses range from 0 (indicating no evidence of the symptom) to 4 (indicating highest severity of symptoms). Possible total scores range from 0 to 67. A symptom is considered positive if a participant had a score of 1 or more for that item.

Verification of alcohol/drug use: Alcohol abstinence will be assessed by self-report, breathalyzer and urine toxicology screens that will be conducted in each appointment during treatment, and on the day of fMRI session.

Assessment for Emotional/Behavioral Problems associated with Addiction:

The following assessments will be administered to assess stress, impulsivity, depression, trauma, and mood symptoms.

The Perceived Stress Scale (PSS); [30] is a 14 item self-report assessing the degree to which situations are appraised as threatening or demanding.

The Spielberger State/Trait Anxiety Questionnaire [31] is a reliable and valid measure of both state and trait anxiety.

The Beck Depression Inventory [32] is regarded as a well-established, sensitive self-report measure of depression

The Center for Epidemiologic Studies Depression Scale (CES-D) (Lewinsohn et al., 1997) a screening test for depression and depressive disorder.

The Emotion Regulation Scale (ERS) [33] a 36-item questionnaire to provide a comprehensive measure of the difficulties in emotion regulation.

The Self-Control Scale -Brief (SCS-Brief) (Tangney, 2004) is a 13-item measure of self-control that measures processes that directly involve self-control such as breaking a habit or working toward long-term goals, rather than distal behavioral outcomes of self-control. The SCS-Brief will be administered at intake appointments.

The Barratt Impulsiveness Scale (BIS-11) (Patton et al., 1995) is a questionnaire designed to assess the personality/behavioral construct of impulsiveness.

The Shipley Institute of Living Scale (SHIPLEY) [34] has been widely used to assess cognitive functioning and impairment.

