vi) **Smartphone app survey**: Subjects will respond to smartphone surveys as they go about their daily lives, which may occur in the presence of others. However, smartphones are widely used in public for many tasks by people in everyday life and the completion of the surveys will be brief and relatively discrete. Responses gathered on the smartphones will be encrypted and sent to a secure server. Confidentiality will be maintained to the degree permitted by the technology used. Data will be connected with subject id only. The MetricWire smartphone app has been designed to be compliant with HIPAA regulations. The app encrypts data on participants' phones and while data is wirelessly transferred. The app randomly generates a 24-digit identification code that contains numbers, letters, and remains consistent for each subject throughout the smartphone assessment phase. This identification code will be linked by the research team with the numerical Subject ID that is assigned to subjects upon their initial laboratory visit.

vii) **Alcohol Withdrawal and Abstinence**: Abstinence from alcohol poses a risk of alcohol withdrawal symptoms. As the study requires alcohol abstinence, we will assess alcohol withdrawal symptoms throughout the study period. The risks associated with stopping drinking may include: anxiety, shakiness, confusion, rapid heart rate, fever and in rare cases, life-threatening seizures. In addition, if participants are unable to make an effort to stay abstinent from alcohol during the study, they may be withdrawn from the study.

11. Minimizing Risks: Describe the manner in which the above-mentioned risks will be minimized.

See above

The PI and all members of the research team have or will have taken the Human Investigations Training Course either on-line (through the NIH) or in person through the Yale University School of Medicine. All clinical research

procedures will be performed by trained research and clinical staff, at the YSC and MRRC. In the event of an injury, medical therapy will be offered to the volunteer with the cost incurred by the subject's medical insurance carrier.

Risks Associated with MRI data collection: Subjects will be screened for the presence of any metallic prostheses or ferromagnetic metal prior to MR imaging. If the subject has any metallic prostheses, they will be excluded from the study. If a subject becomes anxious during the scan, they can request that the MRI scan be stopped.

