Risks Associated with any Psychological Discomforts during Study Procedures: The PI is a trained psychologist who has extensive clinical and counseling experience with patients with AUD and trauma. The proposed project will be conducted at the Yale Stress Center (YSC), and the YSC research and clinical team has extensive expertise in working with clinical populations. The research and counseling facilities of the Yale Stress Center includes clinical and research professionals trained in psychology, cognitive behavioral therapy, contingency management and counseling for client and patients. The PI, as well as research and clinical professionals with expertise in trauma and emotional difficulties will be on-site during the conduct of all study procedures. The PI will be present at (or on call for) all intake and experimental sessions and will be available to consult on issues of what constitutes imminent risk and to guide procedures for referrals as needed.

Risks Associated with Alcohol Withdrawal and Abstinence: Alcohol withdrawal symptoms will be monitored by research staff throughout the study period. Subjects showing moderate to severe clinical signs of alcohol withdrawal, will be either referred to alcohol detoxification treatment or admitted to the CNRU for a brief stay. The CNRU is a clinical inpatient psychiatric facility fully equipped to manage alcohol detoxification, and detoxification will usually last between 1 to 4 days. The detoxification treatment protocol is not part of this research study and a subject's decision to take part in the research study will have no effect on their clinical treatment at the CNRU. CNRU is a state-run facility and provides free treatment for patients for CNRU principal investigators. One of co-investigators of this project, is a CNRU principal investigator, therefore, CNRU treatment will be provided with no cost.

Confidentiality: All data will be kept confidential except in cases of imminent danger to the participants. Such limits to confidentiality will be clearly explained to participants verbally and in the written consent forms.

Confidentiality regarding collected materials will be maintained via a numbered reference system maintained by the investigators. Subjects' names will appear only on a consent form and a "key" form kept by the PI in locked filing

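### Does the impossible CIWA-Ar score range (13 items scored 0 to 4, total up to 67) put withdrawal monitoring or any analysis at risk?

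*Combined protocol and SAP*

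**What the plan says.** In Section I, 4. Research Plan, under the assessments for alcohol use and addiction, the protocol names one withdrawal instrument: "Alcohol withdrawal will be measured using the Clinical Institute Withdrawal Assessment of Alcohol Scale, Revised (CIWA_Ar". It then describes it in four statements.

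- Length: "CIWA-Ar is a 13-item interviewer guided measure to evaluate current alcohol withdrawal (AW) signs and symptoms".
- Item scoring: "Item responses range from 0 (indicating no evidence of the symptom) to 4 (indicating highest severity of symptoms".
- Total: "Possible total scores range from 0 to 67".
- Scoring rule: "A symptom is considered positive if a participant had a score of 1 or more for that item".

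Two later places concern withdrawal. Section 10 (Risks), item vii, says: "As the study requires alcohol abstinence, we will assess alcohol withdrawal symptoms throughout the study period". Section 11 (Minimizing Risks) gives the action: "Subjects showing moderate to severe clinical signs of alcohol withdrawal, will be either referred to alcohol detoxification treatment or admitted to the CNRU". Neither names the CIWA-Ar or gives a score. Section 12 (Data and Safety Monitoring Plan) cites possible withdrawal symptoms during outpatient treatment as a reason for not rating the risk as minimal.

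**The concern.** A scale of 13 items capped at 4 cannot reach 67, so at least one of the three figures is wrong. If a data-capture form were built literally from this paragraph, a patient with the worst possible signs would score 52 on a scale that readers believe runs to 67. Anyone judging severity against bands drawn on the longer range would place that patient too low. Withdrawal can be dangerous (section 10 mentions rare life-threatening seizures), and the CIWA-Ar is the only withdrawal measure the protocol names. A mis-scaled score could therefore mean that a patient who should be referred or admitted is missed.

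**Working it through.** **Inputs**, all from the CIWA-Ar paragraph in the Assessments section: number of items k = 13; item minimum 0; item maximum m = 4; stated maximum total 67.

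**Step 1. Try to reproduce the stated maximum.** Maximum total = k × m = 13 × 4 = 52. The stated 67 is not reproduced. The gap is 67 − 52 = 15 points, and 15/67 = 22.4%.

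**Step 2. Look for a reading that saves all three figures.**

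| Reading | Maximum total |
|---|---|
| 13 items, 0 to 5 (or coded 1 to 5) | 65 |
| 13 items, 0 to 6 | 78 |
| 14 items, 0 to 4 | 56 |
| 16 items, 0 to 4 | 64 |
| 17 items, 0 to 4 | 68 |

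Thirteen equal items would need a maximum of 67/13 = 5.15 each. Items scored 0 to 4 would have to number 67/4 = 16.75. Neither is a whole number. The paragraph mentions no weighting, no item with a wider range and no subset of items. The contradiction is real, and nothing elsewhere in the document resolves it or shows which figure is wrong. The value 52 is only what the first two figures imply, not a corrected maximum.

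**Step 3. Ask where the 22% would act.** For a recorded total T, the share of the maximum is T/52 or T/67. Their ratio is 52/67 = 0.776, so the second is 22.4% lower. This matters only if someone divides T by the maximum or uses bands set on the 67-point range. The protocol does neither: it describes a plain sum, and T itself does not depend on the maximum printed in the protocol.

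**Step 4. Take each possible source of the error in turn.**

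- Only the 67 is wrong: sums of 13 items scored 0 to 4 are correct as recorded.
- The 0-to-4 sentence is loose and the form allows wider responses: sums from the form are correct as recorded.
- The item count is wrong: the form carries its own items, and its sums are correct as recorded.
- The form itself was built to the wrong figures: if the cap of 4 is what is wrong, totals lose points, but only on items that would have exceeded 4. The document gives no sign that this happened and no basis for how often such responses would occur.

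**Step 5. Trace every stated use of the scale.**

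| Place | What it uses | Depends on the maximum total? |
|---|---|---|
| Assessments, positivity rule | Item score of 1 or more | No |
| Section 8, eligibility | CIWA-Ar not mentioned | No |
| Section 10, item vii | Symptoms assessed, no scale or score given | No |
| Section 11, referral or admission | Moderate to severe clinical signs, no scale or score given | No |
| Section 13, Aims 1 to 3 | CIWA-Ar not named as outcome, predictor or covariate | No |

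One indirect route remains. The Aim 3 Cox model adjusts for clinical measures found to predict relapse, and a withdrawal score could be among those examined. A covariate enters the model through its recorded values; the maximum printed in the protocol plays no part.

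**The case for a change.** The strongest case for acting is that this is the only withdrawal instrument named, that withdrawal drives the risk rating, and that staff and form builders work from the protocol. A moderate-to-severe judgement has to be made somehow, and the named scale is the natural tool. Whichever figure is wrong, the text misleads someone, and correcting it costs almost nothing.

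Much of this stands. The arithmetic is exact, the sentences are complete prose rather than a damaged table, and it is plausible that staff look at the CIWA-Ar when judging signs. What does not stand is the step to harm. It needs a form rebuilt from one descriptive paragraph, severity bands on a 67-point range that appear nowhere in the document, and a decision tied to those bands. The Assessments section says that established measures are used, and it cites a published source for this one, so a slip in the description is at least as likely as a mis-built form. A call to re-score patients assumes an error that has not been shown, and responses cut off by a cap could not be recovered from the recorded data.

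**Conclusion.** The description contradicts itself by 15 points (52 against 67), and that is certain. It is a clerical slip: no stated eligibility rule, safety action, outcome or analysis uses the total or its maximum, so correcting the paragraph alters no decision or result. The three figures must be reconciled with the version of the instrument in use, and a glance at the data-capture form would confirm that it matches. That is ordinary text maintenance rather than a change to the plan. Neither the 22% understatement nor a mis-scaled safety trigger can be claimed from these documents.

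The conclusion rests on two assumptions: that the form in use follows the published instrument rather than this paragraph, and that no score threshold is applied outside the documents. If a threshold on the total were in use, the point would need to be looked at again.
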